#### Data Reporting

Data reporting will be performed utilizing the eVelos electronic data capture system. Prior to study initiation, all participating sites must have eVelos users registered and trained on use of the system. The University of Chicago CRA will provide each site with the applicable user registration information.

All required data must be recorded in the eVelos database at the completion of each cycle. AEs are to be entered in real time. SAEs are to be entered on the Serious Event Form within 24 hours of the site's knowledge of the event and sent via email (preferred) or fax to the University of Chicago ([contact] or [contact]; [contact]). All case report forms must be completed by designated study personnel. Each screened (consented) patient is to be entered into eVelos within 48 hours of patient registration. In addition to direct data entry, you may be required to provide supporting source documentation. Source records are original documents, data, and records (e.g., medical records, raw data collection forms, pharmacy dispensing records, recorded data from automated instruments, laboratory data) that are relevant to the clinical trial. Each site will prepare and maintain adequate and accurate source documents. These documents are designed to record all observations and other pertinent data for each subject enrolled in this clinical trial. Source records must be adequate to reconstruct all data transcribed onto the case report form.

## 6.4 After Registration

### *Biomarker Studies*

As exploratory endpoints of this trial, we propose retrospective tumor testing of (1) EGFR and/or HER2 expression status; (2) epithelial to mesenchymal transition states; (3) novel microRNAs since they may relate to response rates in this study; (4) post hoc investigational/confirmatory testing of specific somatic genomic alterations to understand the role of specific alterations in drug sensitivity; and (5) investigation of germline pharmacogenomic determinants that may be associated with drug activity and/or toxicity. These analyses (and the requested research tissues) are separate from those required for study eligibility.

For each registered patient, the enrolling institution will pursue and obtain archival tumor tissue from the patient's primary urothelial cancer surgery. Patients will be asked to consent to release of this tissue during enrollment. For these exploratory biomarker studies, if a patient's tumor is not able to be located, this does not make the patient ineligible for the study, however, full attempts at procurement of this tissue for all enrolled patients is mandatory. The following archival tissue types are needed (one from each below category is needed):

1. 10 unstained slides cut at 5 microns for IHC purposes.

AND

2. Paraffin blocks containing a tumor specimen measuring at least 0.5 cm x 0.5 cm x 100 microns; OR 15-20 additional unstained slides cut at 10 microns; OR 8-10 core needle tissue punches of the tumor region deposited in a microcentrifuge tube.

Tissue samples may be from original diagnosis or biopsy any time prior to first drug treatment, and as long as from a muscle-invasive or higher-stage urothelial cancer specimen (metastatic is permitted). Securely label the specimens with the patient's initials, registration number, and study number (University of Chicago IRB#). Submitted tissues should be sent in a dry container at room temperature, boxed and labeled appropriately.

Additionally, a single peripheral venous blood sample will be collected from each registered patient for the purposes of germline DNA extraction and potential future exploratory pharmacogenomic testing. Whole blood (totaling 10 mL) should be drawn at one timepoint into ONE, 10 mL plastic lavender top tube (i.e. BD catalog # 366643). Whenever possible, this blood draw should occur in conjunction with other standard of care phlebotomy. The tube should be labeled with the patient's ID#, initials, assigned study ID, date and clock time of sample acquisition. The Pharmacogenomic Sample Sheet (APPENDIX 5) should be completed and provided with the samples.

The above samples described in this Section, Section 6.4, should be sent by overnight delivery to:

Attn: [name]  
Lab: [name] (PI)

[name]  
The University of Chicago  
[name]

Please notify [name] by e-mail on the day of mailing at:

[[contact]](mailto:[contact])

## **6.5 Treatment period(s)**

A cycle will be defined as 56 days (8 weeks) of continuous daily therapy. Treatment may continue indefinitely in the absence of disease progression or unacceptable toxicity.

## **6.6 End of study treatment and follow-up period**

All patients must be seen for an end of study visit to occur 28 days following their date of treatment discontinuation. Patients will thereafter be followed at a minimum of every 3 months until the patient dies or refuses further follow up, or until three years of follow up are reached.

# **7. STATISTICAL METHODS**

## **7.1 PLANNED ANALYSES**

### **7.1.1 Primary analyses**

This is a continuation of a single-arm phase II study. The previous phase of this study allowed enrollment of patients without respect to genomic marker status ('non-marker selected population'). That prior phase has been fully accrued (total n=23 patients), completed, and has been analyzed separately per the original statistical plan.

The present continuation portion of this phase II trial will enroll only patients whose tumors harbor genomic alterations in one or more of the *ErbB* family genes. This will comprise the 'marker-selected population' of this continuation trial.

In a meta-analysis of second-line clinical trials in patients with advanced urothelial carcinoma, the overall estimated progression-free survival (PFS) rate at 6 months was 22.6% (95% CI: 18.8%-25.9%), although it varied from 34.6% in patients with no risk factors (liver metastases, ECOG 1+, Hb<10 g/dl, or time from previous chemotherapy <6 months) to 4.9% in patients with 3-4 risk factors. Thus over three-quarters of patients will have disease progression within 6 months, and we propose that PFS at 6 months would be an informative endpoint for assessing drug activity.

For this continuation (marker-selected population) phase, a Simon, optimal two-stage design will be employed to assess the primary end point of 6-month PFS rate. The null hypothesis ( $H_0$ ), a 6-month PFS of <25%, will be considered representative of lack of efficacy of the drug in this biomarker-specific patient population consisting of patients with *ErbB* alterations. The alternative hypothesis ( $H_A$ ), a 6-month PFS rate of >40%, will be

considered indicative of activity. PFS will be defined as the time from enrollment until disease progression or death from any cause, and will be estimated using the Kaplan-Meier method, although we will follow the last patient entered for a minimum of 6 months to ensure that there is no censoring prior to 6 months. For determination of the PFS curve, patients who are alive and progression-free will be censored as of the date of the last negative evaluation.

For 90% power at one-sided alpha = 0.10, n=72 patients will be needed. Assuming the frequency of having an alteration in any of the four genes is 20%, this will require screening approximately 360 patients. In the first stage, 29 patients will be enrolled and if 7 or fewer are alive and progression-free at 6 months the trial will be terminated for futility. Otherwise an additional 43 patients will be enrolled. At the end of the second stage, if 22 or fewer are alive and progression-free at 6 months the null hypothesis will be accepted and the treatment considered to be of insufficient efficacy, whereas if 23 or more (> 32%) exhibit progression-free survival of 6 months or more the regimen will be considered promising and worthy of further study.

Vinflunine is approved for use in urothelial cancer patients in the second-line setting in Europe. Separately, atezolizumab, nivolumab, durvalumab, and pembrolizumab have recently been FDA approved and/or studied in this setting as well and have shown significant activity despite not showing demonstrable changes in PFS. We therefore contend that our chosen 6-month observed PFS rate of 32% or higher required to consider afatinib promising would compare afatinib very favorably in this disease. This level of activity would warrant consideration of further testing of afatinib in this disease and biomarker subgroup.

We also considered in this statistical plan whether there are any relevant data about progression free survival in the subset of patients with *ERBB* alterations? Our prior data (from the first 23 patients of this trial) is the largest cohort we are aware of reporting PFS data in patients with different types of *ERBB*-altered tumours. However, two other prior studies may be additionally indirectly informative. Powles et al. recently examined 232 patients with metastatic urothelial cancer who had undergone primary platinum-based chemotherapy and were then randomly assigned to lapatinib vs placebo. To be randomized, patients had to have “high expression” of HER1/2 (defined as immunohistochemistry 2+/3+ staining). While genomic alteration status was not reported in this study—making these data only tangentially pertinent to the present question—it is reasonable based on known correlation data between IHC and genomic amplification to assume that the trial would have included a higher portion of patients with true amplification than an entirely unselected metastatic urothelial cancer population. The authors found no difference in PFS between patients randomized to lapatinib (4.5 months) vs placebo (5.1 months). These PFS estimates correlate extremely well with the meta-analysis data that we have cited above (see also Sonpavde et al.—data which showed 4.3-4.5 months as the estimated “PFS” for the immediate post-platinum setting in the absence of treatment). While not directly answering the question of a truly *ERBB*-altered population, the Powles et al. data therefore suggest that PFS is not significantly different in HER1/2-overexpressing patients compared to historical controls.

More relevant are the data from Fleischmann et al. which reported on 150 patients who had undergone cystectomy and were followed for survival. The primary tumours of these patients were assessed for *HER2* amplification. Twelve (12) patients were found to be *HER2* amplified. While PFS data are not reported, it was interestingly noted that overall survival was significantly *poorer* in patients with *HER2* amplified tumours (with an absolute shortening of overall survival by approximately 1 year;  $p=0.04$ ). It would follow that PFS is also likely to be shorter (tracking with OS) in this genomic population. This would mean that the historical PFS estimate used in our study (which included all urothelial cancer patients notwithstanding genomic status) is, if anything, likely an over-estimate of the actual PFS of patients with *ERBB* alterations. We thus feel that our historical comparator assumptions in this statistical plan in fact thus set a very high bar (perhaps even higher than may be truly present for this genomic population, although the above data are very limited). This means that the success endpoint for detecting an effect of afatinib on PFS is likely very stringent, or, said another way, the above data do not suggest that the study design has an inherent bias in favor of detecting the effect (if anything, the bias is in the other direction).

We would also argue that one of the potential values of our proposed selected cohort-expansion study will be to better define the PFS in this only-recently appreciated population of patients.

Secondly, afatinib treatment in the context of this trial will most likely be used as a “third line” therapy given the advent and FDA approval of immunotherapies in the traditional “second line” setting. We therefore examined recent data on immune therapy-treated patients to ensure that the above PFS estimates remained reasonable.

First, none of the studies which have reported on the impressive activity of immunotherapies in the platinum-refractory setting for urothelial cancer have shown an impact on PFS compared to historical controls. In fact, even in the landmark phase III pembrolizumab vs cytotoxic chemotherapy study for platinum-refractory patients—which is the only study to show in a prospective, randomized fashion an overall survival benefit for immunotherapy in urothelial cancer—the PFS was not different between the two arms (median 2.1 months in the pembrolizumab arm and 3.3 months in the cytotoxic arm, HR 0.98 [0.81-1.19];  $P=0.42$ ). The PFS6 rate in both arms was approximately 26%. These PFS times compare very favorably to the estimates used to define our historical comparator estimate in the above statistical plan. Additionally, in the *NEJM* phase III trial, 115 of the 542 (21%) randomized patients were indeed actually receiving the pembrolizumab or comparator cytotoxic chemotherapy in the “3rd line”, so the PFS estimates reported above in this paragraph from that trial do reflect the best available data from both “2nd” and “3rd” line populations.

Secondly, Sonpavde et al. recently published cancer progression and survival data for patients in the post-PD-1/PD-L1 setting. Reporting data from 62 patients across 4 institutions, the median time from last PD-1/PD-L1 inhibitor therapy to subsequent therapy (a mark which approximates the “PFS”, or the progression-free interval in the absence of ongoing treatment after immune therapy) was 58 (range 14-242) days. Additionally, of the 22/62 patients who received post-PD-1/PD-L1 inhibitor therapy, the median time to progression (on subsequent therapy) was 124 days. Both of these “3rd line” estimates overlap with the confidence

interval for the PFS data from the “second line” meta-analysis that was used for the above statistical assumptions.

These aggregate external data suggest therefore that the statistical assumptions around PFS and PFS6 remain very reasonable and robustly reproducible estimates to use in the above afatinib statistical plan.

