## FLOW CHART

Study Period	Screening*	Cycle 1 ** A		Cycle 2 ** A		Subsequent Cycles (3, 4, etc.) ** A	End of Treatment and Post-Study treatment		
Visit Days	Day -21 through day 0	Day 1 ‡ C	Days 15, 29, and 43 ‡	Day 57(C2D1) ‡	Days 15 and 29 ‡	Days 1 and 29 ‡	EOT ‡	FU ‡	Add. FU ¶ ‡
Informed consent	X								
Demographics	X								
Medical history	X								
Concurrent meds	X	X		X		X	X		
Documentation of qualifying somatic genomic molecular alteration in EGFR , HER2 , ERBB3 , or ERBB4	X								
Physical exam	X	X C	X	X	X	X	X	X	
Vital signs including O 2 sat	X	X	X	X	X	X	X		
Height	X								
Weight	X						X		
Performance status	X						X		
CBC w/diff, plts	X	X C	X	X	X	X	X		
Serum chemistry#	X	X C	X	X	X	X	X		
Serum BHCG ¶	X								
MUGA £	X				X £	X £			
Dispense study drug to subject		X ¶		X ¶		X ¶			
Radiologic evaluation (CT or MRI)	X			X		X B	X B§		
Tumor measurements	X			X		X B	X		
Adverse event evaluation	X	X	X	X	X	X	X	X	
Archival research tumor tissues %	X --->	-->	--> X						
Pharmacogenomic blood sample	X --->	-->	--> X						
Survival status							X	X	

---

IRB13-0540/ 1200.171

Protocol Version: 10/22/18 v.15

\*Baseline evaluations, including imaging studies, are to be conducted within 21 days prior to start of protocol therapy.

% Archival tissues to be used for exploratory biomarker research studies described in Section 6.4. These research tissue samples are not required for eligibility nor registration and may be submitted during screening or after registration but must be received by the end of cycle 1. See section 6.4 for details.

\*\* Treatment courses continue until disease progression or unacceptable drug intolerance.

#Comprehensive metabolic panel (Na, K, Cl, HCO3, BUN, Creatinine, Glc, Ca, Total Bilirubin, Total Protein, Albumin, AST, ALT, Alkaline Phosphatase), Mg, PO4

¥ BHCG = beta human chorionic gonadotropin. Only required in women with intact uterus. If elevated, pt ineligible unless pregnancy otherwise proven to be excluded.

A: Each cycle is 56 days in length.

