¶ Patient supplied with two bottles of study drug on day 1 of each 56-day cycle. Each bottle contains 30 tablets. See Section 4.3 for adherence reporting requirements (pill counting/pill diary).

‡ (+/-) 4 day visit window

C: It is encouraged that patients for whom a treating physician feels may be at higher than average risk for toxicity from afatinib should be seen at one extra in-person visit, 1 week after starting study therapy (on cycle 1 day 8). This visit should include physical exam and CBC with diff, plts and serum chemistry assessment.

£ MUGA (multi-gated acquisition scan) must also be performed every 12 weeks during therapy B: Radiographic assessment of responses to be performed every 8 weeks until disease progression is observed or until drug intolerance.

EOT = end of treatment

§ A scan performed for clinical reasons mid-cycle (e.g., for clinical symptoms of possible disease progression) which indeed confirms progressive disease and which results in the patient being taken off study, will count as the EOT radiologic evaluation.

FU = follow-up

Add FU = additional follow-up

¶Patients should be followed for 3 years after end of treatment

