### **5.2.4 Assessment of other safety parameters**

#### **5.2.4.1 Physical examination, performance score**

A physical examination will be performed at screening and at the time points specified in the Flow Chart.

A full physical exam serves as a clinical tumor assessment and should include a cardiopulmonary examination and an assessment of the mental and neurological status. Additional symptoms which have not been reported during a previous examination should be clarified. Wherever possible the same investigator should perform this examination.

Measurement of height (in cm), body weight (in kg) and body temperature and the evaluation of the ECOG performance score will be performed at the time points specified in the Flow Chart.

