## **6.3. REGISTRATION PROCEDURES**

### **6.3.1 General Guidelines**

All eligible patients will be registered centrally by the University of Chicago Clinical Research Associate assigned to the study. All sites should call the CRA to verify availability of a slot. Following registration, patients should begin protocol treatment within the window specified in 6.2.1. Issues that would cause treatment delays should be discussed with the Lead Principal Investigator. If a patient does not receive protocol therapy following registration, the patient's registration on the study may be canceled. The CRA should be notified of cancellations as soon as possible.

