- The date the patient is randomized if randomization is involved or receives treatment for the first time will be considered the patient's "OnStudy Date." The patient's subject ID will be assigned and a confirmation of registration will be issued by the CRA on this date. Subjects that sign consent and do not go "OnStudy" will be recorded in the database with the date they signed consent and the reason for not going "OnStudy" (e.g., Ineligible, Screen Failure or Withdrawn Consent).

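### Six months of minimum follow-up does not by itself rule out censoring before 6 months on the PFS curve; separately, 23 of 72 is 31.9%, not above 32%

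*Combined protocol and SAP*

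**What the plan says.** Section 7.1.1 sets the time origin and the events: "PFS will be defined as the time from enrollment until disease progression or death from any cause". It plans a Kaplan-Meier estimate and adds that "we will follow the last patient entered for a minimum of 6 months to ensure that there is no censoring prior to 6 months". The following sentence reads "For determination of the PFS curve, patients who are alive and progression-free will be censored as of the date of the last negative evaluation".

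The Flow Chart footnotes fix the evaluation calendar: "Radiographic assessment of responses to be performed every 8 weeks until disease progression is observed or until drug intolerance", "Each cycle is 56 days in length", and a visit window of 4 days either way. From cycle 3 the Flow Chart places physical exams on days 1 and 29 of each cycle. Section 5.2.4.1 gives these exams some standing as evaluations: "A full physical exam serves as a clinical tumor assessment".

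On when enrollment happens, section 6.3.1 says "Following registration, patients should begin protocol treatment within the window specified in 6.2.1", and section 6.2.1 gives a 21-day window. Section 6.3.2 (Treatment Registration) ties registration to the day of first treatment: "a confirmation of registration will be issued by the CRA on this date".

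The decision rule in section 7.1.1 is a count. The trial stops with 7 or fewer successes among the first 29 patients, and the drug is promising with 23 or more of 72. The synopsis and section 7.1.1 label that threshold as more than 32%. Section 7.1.1 later describes it as 32% or higher.

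**The concern.** Under the censoring sentence, a progression-free patient contributes time only up to the last negative evaluation. A minimum length of follow-up therefore prevents early censoring only if an evaluation falls at or after 6 months and before the data are cut. If none is scheduled there, the two adjacent sentences in section 7.1.1 conflict. The Kaplan-Meier estimate at 6 months would then rest partly on censored patients, although the plan says there will be none.

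The percentage label is a separate matter. A label stricter than the count invites someone to apply it literally and move the threshold by one patient.

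**Working it through.** **1. The plan's own design.** Inputs from section 7.1.1: null 25%, alternative 40%, n1 = 29, stop at 7 or fewer, n = 72, reject at 23 or more.

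P(reject | p) = sum over x = 8 to 29 of Bin(x; 29, p) × P[Bin(43, p) ≥ 23 − x].

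- p = 0.25: 0.0977.
- p = 0.40: 0.9011.

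This agrees with the stated one-sided alpha of 0.10 and power of 90%. A search for the Simon optimal design returns the same four numbers (29, 7, 72, 22).

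**2. The label.** 23/72 = 31.94%. Since 0.32 × 72 = 23.04, both more than 32% and 32% or higher would literally need 24 of 72 (33.33%). With 24 in place of 23 in the formula above, alpha is 0.0635 and power 0.8709.

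**3. The evaluation calendar, in days after first dose.**

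- Week-24 scan and exam: 3 × 56 = 168 (164 to 172 with the window).
- Next exam, cycle 4 day 29: 168 + 28 = 196 (192 to 200).
- Week-32 scan: 4 × 56 = 224 (220 to 228).

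Nothing is scheduled between day 172 and day 192, even if exams count as evaluations.

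**4. The gap.** The documents do not define 6 months in days, so the range is shown. Gap = length of 6 months − day of the week-24 scan, with time counted from first dose.

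| Reading of 6 months | Days | Scan at day 164 | Scan at day 168 | Scan at day 172 |
|---|---|---|---|---|
| 28-day months | 168 | 4 | 0 | none |
| 30-day months | 180 | 16 | 12 | 8 |
| Calendar months | 182.6 | 18.6 | 14.6 | 10.6 |

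**5. Time origin.** PFS runs from enrollment. On calendar months, a lead of 14.6 days between enrollment and first dose would put a day-168 scan at 6 months (10.6 days for a scan at day 172, 18.6 for one at day 164). Section 6.3.1 allows such a lead. Section 6.3.2, which confirms registration on the day of first treatment, does not assure it.

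**6. Effect on the curve.** Suppose 24 of 72 patients are progression-free at week 24, k of them are censored there, and e events occur among the others before 6 months. Then

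S(6 months) = (24/72) × [1 − e/(24 − k)].

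The values of 24, k and e are assumptions; the documents give neither an accrual rate nor a final cut date.

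| e | k = 0 | k = 1 | k = 5 |
|---|---|---|---|
| 0 | 33.33% | 33.33% | 33.33% |
| 1 | 31.94% | 31.88% | 31.58% |
| 2 | 30.56% | 30.43% | 29.82% |

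The shift is zero with no event in the gap, 0.06 to 0.36 points with one event, and 0.13 to 0.74 points with two.

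**The case against.** The strongest reply is that no section plans a final cut at exactly 6 months; the text gives a minimum. The synopsis runs the study until treatment has ended and data are collected. Section 6.6 follows patients at least every 3 months for up to three years. Section 7.1.2 continues follow-up for PFS after treatment stops, and section 10.3.1 places the study report after the last follow-up visit. This stands, and it makes the gap unlikely to matter in practice. It does not rescue the claim that the 6-month floor itself ensures no censoring.

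It can also be said that section 6.1 uses monthly for visits that the Flow Chart places 28 days apart, so 6 months might be read as 168 days. On that reading only a scan done up to 4 days early leaves a gap. This stands as one end of the range.

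A reader might infer that the interim analysis has the same defect. The documents do not support this. The interim uses a count, and patients qualify by completing treatment or by reaching 6 months without being taken off it. Section 3.3.4 lists progression among the criteria that end treatment. No censoring rule enters.

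On the label, 31.94% rounds to 32% and the integer rule is explicit. That is why it is only a wording correction.

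**Conclusion.** The point holds, and it is minor. If 6 months means 180 to 183 days from first dose, a progression-free patient followed only for the stated minimum is censored about 8 to 19 days before 6 months. If it means 168 days, the gap survives only for an early scan. If enrollment precedes first dose by about two weeks, it closes.

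The consequence is limited to the Kaplan-Meier estimate at the final analysis, and to patients whose data are cut before their next evaluation.

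Three stronger conclusions might be inferred, and none is supported:

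- **Loss of power or a changed go/no-go decision.** The two-stage rule counts patients and does not use the censoring sentence, so alpha stays at 9.8% and power at 90.1%.
- **Agreement of curve and count once the gap is closed.** Section 7.2 counts withdrawal from therapy before 6 months as failure, whereas section 7.1.1 defines PFS events as progression or death. The two can differ with no censoring at all.
- **A threshold of 24 patients.** The count of 23 is explicit and governs; only the percentage beside it is wrong.

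**What to change.** In section 7.1.1, do one of two things:

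- Set the minimum follow-up for the final Kaplan-Meier analysis to include the last patient's week-32 scan, which is already scheduled. On calendar months the wait beyond 6 months is at most 224 − 182.6 = 41 days, or 45 with the 4-day window, so about six weeks. It applies only if patients have not yet reached that scan.
- Delete the statement that the minimum follow-up ensures no censoring before 6 months. This costs only the edit.

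In either case, state whether time runs from registration or from first dose, and preferably how many days make 6 months. Leave the interim timing and the section 7.2 failure rule as they are. In particular, do not define success as a negative week-24 scan with no event by 6 months: a patient who then withdrew from therapy before 6 months would be a success under that wording and a failure under section 7.2.

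Separately, write 23 or more of 72 (31.9%) in the synopsis and at both places in section 7.1.1, and say that the count governs. This changes no decision and costs nothing beyond the edit.
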